#### 8.4 Dose modifications for dexamethasone based on adverse events during a cycle

CTCAE System/Organ/Class (SOC)	ADVERSE EVENT	AGENT	ACTION**
Gastrointestinal disorders	Dyspepsia Grade 1 or 2 or Duodenal ulcer Grade 1 or 2 or Gastric ulcer Grade 1 or 2 or Gastritis Grade 1 or 2	Dexamethasone	Treat with H2 blockers, sucralfate, or omeprazole. If symptoms persist despite above measures, decrease dexamethasone dose by 1 dose level.
	Dyspepsia $\geq$ Grade 3 or Duodenal ulcer $\geq$ Grade 3 or Gastric ulcer $\geq$ Grade 3 or Gastritis $\geq$ Grade 3	Dexamethasone	Omit dexamethasone until symptoms adequately controlled. Restart one dose level below along with concurrent therapy with H2 blockers, sucralfate, or omeprazole. If symptoms persist despite above measures, discontinue dexamethasone and do not resume
	Pancreatitis $\geq$ Grade 3	Dexamethasone	Discontinue dexamethasone and do not resume
General disorders and administration site conditions	Edema limbs $\geq$ Grade 3 or Edema trunk $\geq$ Grade 3	Dexamethasone	Diuretics as needed, and decrease dexamethasone dose by 1 dose level; if edema persists despite above measures, decrease dose another dose level. Discontinue dexamethasone and do not resume if symptoms persist despite second reduction
Metabolism and nutrition disorders	Hyperglycemia $\geq$ Grade 3	Dexamethasone	Treatment with insulin or oral hypoglycemics as needed. If uncontrolled despite above measures, decrease dose by one dose level at a time until levels are satisfactory.
Musculoskeletal and connective tissue disorders	Generalized muscle weakness $\geq$ Grade 2	Dexamethasone	Decrease dexamethasone dose by one dose level; if weakness persists despite above measures decrease dose by one additional dose level. Discontinue dexamethasone and do not resume if symptoms continue to persist
Psychiatric disorders	Confusion Grade $\geq$ 2 OR/And Anxiety Grade $\geq$ 2	Dexamethasone	Omit dexamethasone until symptoms resolve. Restart with one dose level reduction. If symptoms persist despite above measures, discontinue dexamethasone and do not resume.

- \* Located at [REDACTED]
- \*\* Use the following to describe actions in the Action column:
  - Omit = The current dose(s) for the specified drug(s) during a cycle is skipped. The patient does not make up the omitted dose(s) at a later time
  - Hold/Delay = The current dose(s) of all drugs during a cycle is delayed. The patient does make up the delayed dose(s) when the patient meets the protocol criteria to restart drugs.
  - Discontinue = The specified drug(s) are totally stopped.

## **9.0 Ancillary Treatment/Supportive Care**

Medications or vaccinations specifically prohibited in the exclusion criteria are not allowed during the ongoing trial. If there is a clinical indication for one of these or other medications or vaccinations specifically prohibited during the trial, discontinuation from trial therapy or vaccination may be required. The investigator should discuss any questions regarding this with the Merck Clinical team. The final decision on any supportive therapy or vaccination rests with the investigator and/or the subject's primary physician.

All treatments that the investigator considers necessary for a subject's welfare may be administered at the discretion of the investigator in keeping with the community standards of medical care. All concomitant medication will be recorded on the case report form (CRF) including all prescription, over-the-counter (OTC), herbal supplements, and IV medications and fluids. If changes occur during the trial period, documentation of drug dosage, frequency, route, and date may also be included on the CRF.

All concomitant medications received within 28 days before the first dose of trial treatment and 30 days after the last dose of trial treatment should be recorded. Concomitant medications administered after 30 days after the last dose of trial treatment should be recorded for SAEs and ECIs as defined in Section 10.1.

### **9.1 Oral hydration**

Patients are encouraged to drink at least 6 to 8 cups of liquid per day.

### **9.2 Disallowed concurrent treatment**

The following treatments are not permitted during the trial:

- Any other investigational treatment
- Any other systemic anti-neoplastic therapy including, but not limited to, immunotherapy, hormonal therapy or monoclonal antibody therapy.
- Any external beam radiotherapy
- Platelet transfusions to help patients meet eligibility criteria are not allowed within 3 days prior to study drug dosing for any dosing day

#### 9.3 Nausea and/or vomiting

Standard anti-emetics including 5-hydroxytryptamine 3 serotonin receptor antagonists are recommended for emesis if it occurs once treatment is initiated; prophylactic anti-emetics may also be considered at the physician's discretion. Dexamethasone should not be administered as an anti-emetic. Fluid deficit should be corrected before initiation of study drug and during treatment.

#### 9.4 Blood products and growth factors

Blood products and growth factors should be utilized as clinically warranted and following institutional policies and recommendations. The use of growth factors should follow published guidelines of the Journal of Clinical Oncology, Vol 24, No 18 (June 20), 2006: pp. 2932-2947.

#### 9.5 Diarrhea and Ixazomib

Prophylactic antidiarrheals should be used in this protocol. Diarrhea occurring despite the prophylaxis should be managed according to clinical practice, including the administration of antidiarrheals such as loperamide once infectious causes are excluded. Fluid intake should be maintained to avoid dehydration. Fluid deficit should be corrected before initiation of treatment and during treatment. Additional doses of loperamide at 2 mg every 2-4 hours until diarrhea free (maximum 16 mg/day).

In the event of Grade 3 or 4 diarrhea, the following supportive measures are allowed: hydration, octreotide, and antidiarrheals.

If diarrhea is severe (requiring intravenous rehydration) and/or associated with fever or severe neutropenia (Grade 3 or 4), broad-spectrum antibiotics must be prescribed. Patients with severe diarrhea or any diarrhea associated with severe nausea or vomiting **should be hospitalized** for intravenous hydration and correction of electrolyte imbalances.

Please monitor patients carefully for development of ileus.

#### 9.6 Renal failure and Ixazomib

Two cases of acute renal failure have been reported in patients treated at or above the MTD for intravenous ixazomib. Volume depletion should be corrected before initiation of study drug. Until further information is available, intake of nonsteroidal anti-inflammatory drugs immediately prior to the administration of ixazomib should be discouraged and requires consultation with the principal investigator. All necessary supportive care consistent with optimal patient care shall be available to patients as necessary.

#### 9.7 Herpes Zoster prophylaxis

Patients may be at an increased risk of infection including reactivation of herpes zoster and herpes simplex viruses. Prophylaxis with acyclovir 400 mg PO BID is recommended while on study therapy and for 1 month beyond the end of therapy.

## 9.8 Prohibited medications

## 9.81 Prohibited enzyme inducers

Systemic treatment with any of the following metabolizing enzyme inducers should be avoided, unless there is no appropriate alternative medication for the patient's use. (Rationale: If there were to be a drug-drug interaction with an inducer, ixazomib exposure would be less - so there is a reduced chance of an adverse event. However, there may be less chance for an antitumor effect, but that is not an absolute reason to be taken off study):

Strong CYP3A inducers: rifampin, rifapentine, rifabutin, carbamazepine, phenytoin, and phenobarbital.

## 9.82 Excluded foods and dietary supplements include St. John's wort.

## 9.83 Subjects are prohibited from receiving the following therapies during the Screening and Treatment Phase of this trial:

- Antineoplastic systemic chemotherapy or biological therapy
- Immunotherapy not specified in this protocol
- Chemotherapy not specified in this protocol
- Radiation therapy
  - Note: Radiation therapy to a symptomatic solitary lesion or to the brain may be allowed at the investigator's discretion.
- Live vaccines within 30 days prior to the first dose of trial treatment and while participating in the trial. Examples of live vaccines include, but are not limited to, the following: measles, mumps, rubella, varicella/zoster, yellow fever, rabies, BCG, and typhoid vaccine.

Subjects who, in the assessment by the investigator, require the use of any of the aforementioned treatments for clinical management should be removed from the trial. Subjects may receive other medications that the investigator deems to be medically necessary.

The Exclusion Criteria describes other medications which are prohibited in this trial.

There are no prohibited therapies during the Post-Treatment Follow-up Phase.

## 9.9a Erythematous Rash with or without Pruritus

Rash with or without pruritus has been reported with ixazomib, primarily at the higher doses tested and when given with agents where rash is an overlapping toxicity. The rash may range from limited erythematous areas, macular and/or small papular bumps that may or may not be pruritic over a few areas of the body, to a more generalized eruption that is predominately on the trunk or extremities. Rash has been most commonly characterized as maculopapular or macular. To date, when it does occur, rash is most commonly reported within the first 3 cycles of therapy. The rash is often transient, self-limiting, and is typically Grade 1 to 2 in severity.

Symptomatic measures such as antihistamines or corticosteroids (oral or topical) have been successfully used to manage rash and have been used prophylactically in subsequent cycles. The use of a topical, IV, or oral steroid (e.g., prednisone  $\leq 10$  mg per day or equivalent) is permitted. Management of a Grade 3 rash may require intravenous antihistamines or corticosteroids. Administration of ixazomib (and/or other causative

agent if given in combination) should be modified per protocol section 8.3 and re-initiated at a reduced level from where rash was noted (also, per protocol).

In line with clinical practice, dermatology consult and biopsy of Grade 3 or higher rash or any SAE involving rash is recommended. Prophylactic measures should also be considered if a patient has previously developed a rash (e.g., using a thick, alcohol-free emollient cream on dry areas of the body or oral or topical antihistamines). A rare risk is Stevens-Johnson Syndrome, a severe and potentially life-threatening rash with skin peeling and mouth sores, which should be managed symptomatically according to standard medical practice. Punch biopsies for histopathological analysis are encouraged at the discretion of the investigator.

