### 8.1 Dose Levels for each drug in the combination.

	Ixazomib (Days 1, 8, 15, , 29, 36, 43, 57, 64, 71)	Pembrolizumab (200 mg/dose)	Dexamethasone (Days 1, 8, 15, 29, 36, 43, 57, 64, 71)
Starting dose	4 mg	Day 1, 22, 43, 64	40 mg
-1	3 mg	Day 1 and 43	20 mg
-2	2.3 mg	Discontinue	12 mg

\*See Table 8.2 below

**Note: If ixazomib is discontinued, the patient will discontinue pembrolizumab and dexamethasone and go to event monitoring.**

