### 8.11 Instruction for initiation of a new cycle of therapy

A new cycle of treatment may begin on the scheduled Day 1 of a new cycle if:

- The ANC is  $\geq 1000/\mu\text{L}$
- The platelet count is  $\geq 75,000/\mu\text{L}$
- Any other non-hematologic drug-related (possible, probable, or definite) adverse event that may have occurred has resolved to  $\leq$ Grade 1 or baseline severity.

If these conditions are not met on Day 1 of a new cycle, dosing should be delayed for 1 week. At the end of that time, the patient should be re-evaluated to determine whether the criteria have been met. If the patient continues to fail to meet the above-cited criteria, delay therapy and continue to re-evaluate.

If any drug dosing was halted during the previous cycle and was restarted with a one-level dose reduction without requiring an interruption for the remainder of the cycle, then that reduced dose level will be initiated on Day 1 of the new cycle.

If any drug dosing was omitted for the remainder of the previous cycle or if the new cycle is held due to known hematologic toxicity newly encountered on the scheduled Day 1, then the new cycle will be started with a one-level dose reduction. If a new cycle of therapy cannot be restarted within 4 weeks of the scheduled Day 1 due to non-resolution of drug related toxicities, the patient will be removed from protocol therapy and will go to event monitoring.

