### 8.3 Dose modifications for Ixazomib based on adverse events during a cycle

CTCAE System/Organ/Class (SOC)*	ADVERSE EVENT	ACTION**
Investigations	Neutrophil count decreased $<1.0 \times 10^9/L$ or Neutrophil count decreased $>1.0 \times 10^9/L$ (up to LLN) and Fever (temperature $>38.5^{\circ}C$ ) or Platelet count decreased $<30 \times 10^9/L$	Days 2-84: Ixazomib dose should be omitted on Days 1, 8, 15, 29, 36, 43, 57, 64, 71 as applicable Complete blood count (CBC) with differential should be followed weekly If ANC is $\geq 1.0 \times 10^9/L$ and/or platelet counts $\geq 30 \times 10^9/L$ , ixazomib may be reinitiated with 1 dose level reduction. The subsequent cycle will use the reduced dose.
Nervous System Disorders	Newly developed peripheral sensory neuropathy Grade 1 with pain or Peripheral sensory neuropathy Grade 2	Omit until resolution to Grade $<1$ or baseline No dose reduction necessary for this grade
	Peripheral sensory neuropathy with pain Grade 2 or Peripheral sensory neuropathy Grade 3	Omit ixazomib until toxicity resolves or returns to baseline. When toxicity resolves, re-initiate ixazomib at the next lower dose level.
	Peripheral sensory neuropathy Grade 4	Discontinue ixazomib. Peripheral neuropathy should be monitored until toxicity resolves or returns to baseline.
Skin and subcutaneous tissue disorders	Rash, maculo-papular, $\geq$ Grade 2	Omit ixazomib until rash resolves to $\leq$ Grade 1 (See Section 9.9a ). Restart at same dose. If the rash recurs, reduce dose by one dose level.
	Any other skin AE, Grade 4	Discontinue ixazomib and remove patient from all study treatment
	Any other Grade 3 attributable adverse event except: 
 
• Nausea and/or Vomiting Grade 3 in the absence of optimal anti-emetic prophylaxis
 
• Diarrhea Grade 3 that occurs in the absence of optimal supportive therapy
 
• Fatigue Grade 3
 
• Anemia
 
• White blood cell decreased
 
• Lymphocyte count decreased
 
	Omit ixazomib depending on the attribution, until resolution to Grade $\leq 1$ or baseline Restart at next lower dose. If a patient is already at the lowest drug level, go to event monitoring
	Any other Adverse Events Grade 4	Consider permanently discontinuing ixazomib – Exception if the investigator determines the patient is obtaining a clinical benefit

\* Located at [REDACTED]

\*\* Use the following to describe actions in the Action column:

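### For a first maculo-papular rash of Grade 2 or higher, Sections 8.3, 9.9a and 8.11 give conflicting ixazomib restart doses

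*Combined protocol and SAP*

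**What the plan says.** **Section 8.3 (ixazomib dose modifications).** For maculo-papular rash of Grade 2 or higher, ixazomib is omitted until the rash has settled to Grade 1 or less, with a pointer to Section 9.9a. Then: "Restart at same dose. If the rash recurs, reduce dose by one dose level".

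**Section 9.9a (rash, under supportive care).** Ixazomib is to be modified as Section 8.3 directs and "re-initiated at a reduced level from where rash was noted"; a closing parenthesis presents this as the protocol's rule too. The sentence separates neither a first rash from a recurrent one nor one grade from another. The same section says of the toxicity it covers: "Rash has been most commonly characterized as maculopapular or macular".

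**Section 8.11 (starting a new cycle).** If any drug was skipped through to the end of the previous cycle, "then the new cycle will be started with a one-level dose reduction". Rash is not excepted.

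**Table 8.1.** Ixazomib starts at 4 mg, with two lower levels, 3 mg and 2.3 mg. A note under the table says that stopping ixazomib also stops pembrolizumab and dexamethasone and sends the patient to event monitoring.

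**The concern.** Sections 8.3 and 9.9a refer to each other, and the protocol does not say which prevails. An investigator who starts from the table finds one restart dose for a first rash. One who follows its pointer to Section 9.9a finds another, presented there as already being the protocol's rule. Section 8.11 can give a third route to a reduction, depending only on when in the 84-day cycle the rash occurs.

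At stake are the consistency of ixazomib exposure between patients, the meaning of the recorded dose modifications, and how soon a patient uses up the two available steps. Stopping ixazomib ends all study treatment, so the last of these also bears on time on treatment. The event is foreseeable: Section 10.61 has maculo-papular rash graded at baseline and at every evaluation.

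**Working it through.** The plan states no figure to reproduce here. The check is a comparison of the texts, applied to the dose levels in Table 8.1.

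**Step 1. Do the sections cover the same event?** Yes. The Section 8.3 row is for maculo-papular rash of Grade 2 or higher. Section 9.9a describes rash on ixazomib as mostly maculopapular or macular, so its usual case falls in that row once it reaches Grade 2.

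**Step 2. Where do they differ?**

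| Event | Section 8.3 | Section 9.9a | Conflict? |
|---|---|---|---|
| First maculo-papular rash, Grade 2 or higher | same dose | reduced level | yes |
| Recurrence of that rash | one level lower | reduced level | no |
| Other attributable Grade 3 rash | "Restart at next lower dose" | reduced level | no |
| Other skin event, Grade 4 | ixazomib and all study treatment stopped | restart not in question | no |
| Grade 1 rash | row not triggered | no interruption under 8.3, so nothing to restart | no |

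**Step 3. What is the difference in dose?** Section 9.9a does not say how many levels. Assume one.

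- First rash at 4 mg: 4 mg under 8.3, 3 mg under 9.9a. (4 − 3)/4 = 25% lower.
- First rash at 3 mg: 3 mg under 8.3, 2.3 mg under 9.9a. (3 − 2.3)/3 = 23% lower.
- First rash at 2.3 mg: 2.3 mg under 8.3. Section 9.9a points below the lowest level listed.

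**Step 4. Does the difference carry forward?** For a patient starting at 4 mg with one rash and one recurrence, and no other reason to reduce, the sequence is 4, 4, 3 mg under Section 8.3 and 4, 3, 2.3 mg under Section 9.9a. The rule for the recurrence is the same in both, but the first reading has used one of the two steps and the second has used both.

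**Step 5. What does Section 8.11 add?** Suppose a first rash leads only to the Day 71 dose being omitted. That is the last ixazomib dose of the cycle, so Section 8.11 starts the next cycle one level lower. The same rash after Day 8, settled in time for Day 29, restarts at the same dose under Section 8.3. Section 8.11 also mentions hematologic toxicity, but as worded that qualifies the holding of a new cycle, not the skipped doses.

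**Step 6. How many patients?** Section 15.17 lists ixazomib maculo-papular rash at 1% to below 10%, and Section 16.12 plans 37 evaluable patients. 0.01 × 37 = 0.37 and 0.10 × 37 = 3.7, so about 0.4 to below 3.7 patients at any grade. The documents give neither the share reaching Grade 2 nor the rate for the three-drug combination, which could be higher or lower.

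**The case against.** The best defence is that Section 9.9a is subordinate. It sits under supportive care and defers to Section 8.3 by number. Sections 9.9b and 9.9c have the same form: modify per Section 8, then a general line about restarting lower. A reader could take the table as operative and Section 9.9a as loose summary. Section 8.3 also contains genuine reductions, on recurrence and for other Grade 3 events, to which the closing parenthesis in Section 9.9a could refer.

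Part of this stands. A reader might infer that Section 9.9a credits Section 8.3 with a reduction found nowhere in it. That is too strong: the fault is that Section 9.9a does not confine the reduction to the cases where Section 8 requires one. But deference does not remove the conflict, because the same sentence goes on to state a reduced restart, Section 8.3 sends the reader back to it, and no precedence is given. For low neutrophil or platelet counts, the subject of Sections 9.9b and 9.9c, the table does restart one level lower, so there the general line agrees with it. For a first maculo-papular rash it does not.

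It is also fair to say that practice is comparatively centralised. Section 6.16 requires treatment to start at a Mayo Clinic institution, and Section 7.2 rules out treatment by a local doctor. That makes divergent handling less likely, but the instruction remains ambiguous.

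**Conclusion.** Wrong as written: the dosing rule contradicts itself for a first maculo-papular rash of Grade 2 or higher. It should be corrected. The size per event is 25% of the dose at 4 mg and 23% at 3 mg, assuming that a reduced level means one step of Table 8.1. At 2.3 mg, Section 9.9a has no listed level to go to.

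Three stronger readings are not supported.

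- A reader might infer that every ixazomib rash leads to two doses. Recurrent rash and other attributable Grade 3 rash do not.
- A reader might take the frequency of at least 10% listed for rash in Section 15.27 and expect about 4 of 37 patients to be affected. That category is for pembrolizumab, and is not limited to Grade 2 or higher, to maculo-papular rash or to a first episode. The number affected cannot be derived from the documents.
- A reader might infer a bias in the primary response rate. The documents give no relation between ixazomib dose and response from which to size one. Sample size, significance level and power do not depend on this rule. What is shown is a risk of inconsistent exposure and of dose-modification records that mean different things in different patients.

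**What to change.** The sponsor should reconcile Sections 8.3, 9.9a and 8.11 so that one restart instruction governs a first maculo-papular rash of Grade 2 or higher and the other sections only point to it. The governing text should say whether the new-cycle rule in Section 8.11 applies when the skipped doses were due to such a rash. It should also say what is meant by a reduced level, including for a patient already at the lowest level in Table 8.1. Which instruction is right is a clinical decision on which this review takes no position.

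The cost is a short text amendment touching three sections. No change to the design, sample size or analysis follows. If patients have already been treated, restart doses after a first rash should be listed, so that any mixed handling is visible when dose modifications are reported.

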#### 9.9b Thrombocytopenia

Blood counts should be monitored regularly as outlined in the protocol with additional testing obtained according to standard clinical practice. Thrombocytopenia may be severe but has been manageable with platelet transfusions according to standard clinical practice. Ixazomib administration should be modified as noted as per dose modification recommendations in the protocol when thrombocytopenia occurs (see Section 8). Therapy can be reinitiated at a reduced level upon recovery of platelet counts. A rare risk is thrombotic thrombocytopenic purpura (TTP), a rare blood disorder where blood clots form in small blood vessels throughout the body characterized by thrombocytopenia, petechiae, fever, or possibly more serious signs and symptoms. TTP should be managed symptomatically according to standard medical practice.

